## 7. Planned Analyses

The following data analyses are planned:

- (1) Primary analysis after all dose-escalation and dose-expansion subjects had the opportunity to receive up to 12 cycles of treatment or terminated the study early.
- (2) Final analysis after all subjects have ended the study.

Primary and final analysis may be combined in case all subjects have ended study close to the time point of the primary analysis.

### 7.1 Interim Analysis and Early Stopping Guidelines

Safety data will be reviewed on an ongoing basis. Based on accumulating toxicity information, BLRM will be used to make dosing recommendations. In DLRMs, Amgen, in consultation with the site investigators, will review the BLRM recommended dose level and will review all available cumulative data by cohort prior to making dose escalation decisions. As a sensitivity analysis, a one-parameter Continual Reassessment Method (CRM) model may be used to estimate the dose-toxicity relationship to help making dose escalation decisions. Adverse events and DLTs observed in all subjects will be evaluated continually and fully integrated into all DLRMs and considered in all enrollment and dosing decisions.

Ad-hoc interim analysis for efficacy parameters will be conducted after dose escalation is completed. Once preliminary MTD and RP2D are established, FDA will be provided with brief interim results of the dose escalation phase.

#### Dose Level Review Team (DLRT)

DLRMs will be held to review data, monitor safety, and make decisions on dose escalation / change, or changes in pre-medication. If a cohort extension of up to 6 subjects initiates, a DLRT meeting will be conducted after completion of the Japan cohort extension. The DLRT will be composed of the investigators or designees, and the following Amgen representatives: early development leader, global safety officer or designee, clinical study manager, biostatistician, PK scientist (optional), and other functional area representatives as appropriate. The following members are responsible for DLRT decisions: investigators, Amgen medical monitor, and global safety officer or designee. All available study data, including data collected after the initial DLT window, and including demographics, investigational product administration, medical history, concomitant medications, adverse events, ECGs, vital signs, laboratory data, and PK/PD information will be reviewed. In addition to DLTs, all  $\geq$  grade 3 toxicities not meeting DLT criteria will be reviewed and may be considered in DLRT decisions. Modeling of

available potential safety risk data (eg, for thrombocytopenia) to predict safety risk for dose escalation decisions may also be considered.

A quorum as defined below must be in attendance for the DLRM. The quorum is defined as > 50% of the responsible members or their qualified designee (ie, sub-investigator or research nurse or study coordinator possessing written documentation [eg e-mail] of the investigator's vote), as well as > 50% of Amgen representatives listed above. The early development leader or designee must attend for the quorum to be reached. The DLRM will be rescheduled if a quorum is not reached.

The following decisions will be made by the DLRT:

- dose escalation / de-escalation decisions
- administration of additional **doses** on D12 / D19 of a cycle
- number of subjects per cohort
- continuation, delay or termination of dosing
- implementation of dose step(s)
- change of the D1 / D3 / D5 / D12 / D19 dosing scheme within the pre-specified window of  $\pm$  1-3 day
- extension of the treatment-free interval between treatment cycles
- **If grade 5 event is fatal and suspected to be related to investigational product, study may be put on hold if recommended by DLRM.**

Additionally, the DLRT will review safety data for each of the Japan cohort extension subjects, at regular intervals as part of ongoing Dose Level Review Meetings (DLRMs). Subjects' cytogenetic profiles (eg, potentially higher cytokine release in monocytic AML) should be taken into consideration for DLRT decisions.

In the expansion phase, all available study data will be reviewed (with recruitment ongoing) by the DLRT once every 6th subject has at least completed their first treatment cycle plus 2 weeks or dropped out of treatment / study, whichever occurs earlier. Ad hoc meetings may be convened any time in case of important safety events.

**DLRM analysis is based on as-is snapshot including all data up to the data cutoff.**

## 7.2 Primary Analysis

The primary analysis will occur when target enrollment is completed and each subject had the opportunity to receive up to 12 cycles of treatment or terminated the study early.

**Primary analysis is based on locked database.**

### 7.3 Final Analysis

A final analysis is planned after all dose-escalation cohorts and dose-expansion subjects have ended the study. Primary and final analysis may be combined in case all subjects have ended study close to the time point of the primary analysis. **Final analysis is based on final locked database to prevent future change.**

## 8. Data Screening and Acceptance

### 8.1 General Principles

The objective of the data screening is to assess the quantity, quality, and statistical characteristics of the data relative to the requirements of the planned analyses.

### 8.2 Data Handling and Electronic Transfer of Data

The Amgen Global Study Operations-Data Management (GSO-DM) department will provide all data to be used in the planned analyses. This study will use the RAVE database.

### 8.3 Handling of Missing and Incomplete Data

The following imputation for missing or incomplete data will be performed if required: Incomplete adverse event and concomitant medication dates missing data will be imputed as described in [Appendix G](#).

- Non-pharmacokinetic measurements (eg. biomarker data) that are below the lower limit of quantification will be considered equal to half of the lower limit of quantification for all analyses unless specified otherwise.
- Laboratory measurements that are below the quantification limits will be considered equal to the lower limit of quantification for all analyses unless explicitly noted otherwise.
- PK concentrations that are below the quantification limits will be set to zero when engaging non-compartmental model to compute PK parameters

### 8.4 Detection of Bias

Lack of protocol compliance and the potential for biased statistical analyses will be examined by assessing the incidence of important protocol deviations in each cohort. The clinical study team will identify and document the criteria for important protocol deviations.

## 8.5 Outliers

Pharmacokinetic (PK) concentration data will be evaluated for outliers by visual inspection, and decisions to re-assay individual samples will be made in accordance with standard pharmacokinetic evaluation practice.

## 8.6 Distributional Characteristics

Where appropriate, the assumptions underlying the proposed statistical methodologies will be assessed. If required data transformations or alternative non-parametric methods of analyses will be utilized.

## 8.7 Validation of Statistical Analyses

Programs will be developed and maintained, and output will be verified in accordance with current risk-based quality control procedures.

Tables, figures, and listings will be produced with validated standard macro programs where standard macros can produce the specified outputs.

The production environment for statistical analyses consists of Amgen-supported versions of statistical analysis software; for example, the SAS System version 9.4 or later.

## 9. Statistical Methods of Analysis

### 9.1 General Considerations

Descriptive statistics will be provided for selected demographics, safety, PK, PD and biomarker data by dose, dose schedule, and time as appropriate. Descriptive statistics on continuous data will include means, medians, standard deviations, and ranges, while categorical data will be summarized using frequency counts and percentages. Graphical summaries of the data may also be presented. A two-parameter BLRM will be used to estimate the dose-toxicity relationship. Separate BLRM analysis will be conducted for each dose regimen, eg, MTD1 and MTD2 if there is one dose step.

A two-parameter Bayesian logistic regression model (BLRM, [Neuenschwander et al, 2008](#)) is used to guide dose escalation. The MTD target Toxicity Probability Interval (TPI) for DLT is (0.20, 0.33) and TPIs of (0.33, 0.60) and (0.60, 1.00) are defined as excessive and unacceptable, respectively. The design seeks to identify a dose most likely to have a DLT rate in the target TPI, but with overdose control that limits the possibility the dose has an excessive or unacceptable DLT rate ([Babb et al, 1998](#)). The probability of a DLT at dose level  $d_i$  is assumed to follow a Bernoulli distribution with probability  $p_i$  where the logit of  $p_i$  increases linearly with the log of the standardized dose in the following 2-parameter logistic model:

$$\log [p_i / (1-p_i)] = \text{logit}(p_i) = \log[a] + \exp(\log[b]) \log (d_i / d_{\text{ref}})$$

where a and b are random variables and  $d_{\text{ref}}$  is one of the planned dose selected as the reference dose.

A bi-variate normal prior distribution ([Neuenschwander et al, 2008](#)) was selected for  $\theta = (\log a, \log b)$  where the probability that the true DLT rate is  $\leq 0.40$  at  $\blacksquare \mu\text{g}$  is 0.90 and the probability the true DLT rate is  $\leq 0.05$  at the reference dose ( $\blacksquare \mu\text{g}$ ) is 0.05. Additionally, the prior is such that  $p_i$  is approximately 0.05 for the  $\blacksquare \mu\text{g}$  dose and 0.25 for the reference dose. Once the  $\blacksquare \mu\text{g}$  is deemed safe by Dose Level Review Team (DLRT), the reference dose will be updated to the highest planned dose level. **For more details of BLRM, please refer the Appendix H in the protocol.**

## 9.2 Subject Accountability

The number and percent of subjects who were screened, enrolled, received at least one dose of AMG 427, completed investigational product, discontinued from investigational product (including reasons for discontinuing), completed study, discontinued the study (including reasons for discontinuing) will be summarized overall and by dose cohort. Key study dates for the first subject enrolled, last subject enrolled, and last subject's end of study will be presented. A subject listing and summary noting inclusion in each analysis subset will be provided for all subjects enrolled. A subject listing noting, reason for discontinuation of treatment, and reason for discontinuing the study will be provided.

## 9.3 Important Protocol Deviations

Important Protocol Deviations (IPDs) categories are defined by the study team before the first subject's initial visit and updated during the IPD reviews throughout the study prior to database lock. These definitions of IPD categories, subcategory codes, and descriptions will be used during the course of the study. Eligibility deviations are defined in the protocol. **The final IPD list is used to produce the summary of IPDs table and the list of subjects with IPDs. In addition, a separate listing of all inclusion and exclusion deviations will be provided.**

## 9.4 Demographic and Baseline Characteristics

Demographic (i.e., age, age groups [18-64, 65-74, 75-84 and  $\geq 85$ ], sex, race, ethnicity) and baseline characteristics will be summarized by dose cohort and overall using descriptive statistics. If multiple races have been reported for a subject, the subject will be categorized as multiple-race as well as by the combination of race.

## 9.5 Efficacy Analyses

### 9.5.1 Analyses of Primary Efficacy Endpoint(s)/Estimand(s)

NA

### 9.5.2 Analyses of Secondary Efficacy Endpoint(s)

**For R/R AML, the proportion of subjects with an overall response with corresponding exact 80% CI will be calculated using the Clopper-Pearson method ([Clopper and Pearson, 1934](#)) by cohort and tabulated for all subjects treated at the MTD/RP2D. DOR will be analyzed using Kaplan-Meier method. Kaplan-Meier curves and estimates for rates and 80% CI at selected time points will be presented for subjects in dose-expansion cohort. Only subjects with an overall response will be analyzed for DOR. For MRD+ AML, the MRD conversion rate will be presented with corresponding exact 80% CI and tabulated by cohort and for all subjects treated at the MTD/RP2D. Relapse free survival and overall survival will be analyzed using Kaplan-Meier method. Kaplan-Meier curves and estimates for rates and 80% CI at selected time points will be presented for subjects in dose-expansion cohort.**

**[REDACTED]** will be considered exploratory.

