#### Dose expansion cohorts:

- **FIH (R/R AML): approximately 40 subjects**
- **MRD Group (MRD+): approximately 50 subjects**

The sample size in the dose escalation is based on practical considerations and is consistent with conventional oncology studies with the objective to estimate the MTD.

With 2 subjects per cohort, there is a 19% to 55% probability of observing at least 1 DLT. With 3 subjects per cohort, there is a 27% to 70% probability of observing at least 1 DLT if the true DLT rate is 10% to 33% and with 4 subjects per cohort, there is a 34% to 80% probability.

In the dose expansion cohort, a subject number of 40 will provide an 87% probability of observing at least 1 adverse event with 5% incidence rate and 99% probability of observing at least 1 adverse event with 10% incidence rate. **A subject number of 50 will provide a 92.3% probability of observing at least 1 adverse event with 5% incidence rate and 99.5% probability of observing at least 1 adverse event with 10% incidence rate.** These probabilities will be 64% and 88% respectively with a subject number of 20. An exact 80% binomial confidence interval (CI) will be provided for response rate. With the 20 subjects and 20% response rate, the expected 80% CI would be 9% to 36%. With 40 subjects and 20% response rate, the expected 80% CI would be 12% and 30%. **With 50 subjects and a 40% response rate, the expected 80% CI would be 30.6% and 50.1%.**

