### Efficacy Futility Rules during Dose Expansion

During dose expansion, Amgen will conduct evaluations of the ongoing overall response rate to assess if the threshold for early trial termination for futility has been reached. **For R/R AML**, a response consists of any of the following efficacious outcomes: CR, CR with incomplete recovery of peripheral blood counts (CRi), morphologic leukemia-free state,

partial remission and complete response/**remission** with partial hematologic recovery (CRh). An overall response rate less than 15% is considered insufficient efficacy. Amgen proposes stopping enrollment to the dose expansion cohorts early if any of the following occurs.

- None of the initial 12 subjects treated experience a response
- 2 or fewer of the initial 18 subjects treated experience a response
- 3 or fewer of the initial 24 subjects treated experience a response

Using these futility stopping rules, [Table 3](#) shows the probability of early stopping and the average sample size in dose expansion

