**Table 3. Probability of Early Stopping and the Average Sample Size in R/R AML Dose Expansion**

True overall response rate	Probability of early stopping after 12 or fewer subjects	Probability of early stopping after 18 or fewer subjects	Probability of early stopping after 24 or fewer subjects	Average sample size
0.05	0.54	0.94	0.98	15.5
0.10	0.28	0.74	0.82	20.7
0.15	0.14	0.49	0.58	27.0
0.20	0.07	0.28	0.34	32.5
0.30	0.01	0.06	0.07	38.3

[REDACTED]

[REDACTED]. A conversion rate from MRD+ to MRD- < 25% is considered insufficient efficacy. Amgen proposes stopping enrollment to the dose expansion cohorts early if any of the following occurs:

- 2 or fewer of the initial 12 subjects treated experience a response
- 4 or fewer of the initial 18 subjects treated experience a response
- 5 or fewer of the initial 24 subjects treated experience a response

Using these futility stopping rules, [Table 4](#) shows the probability of early stopping and the average sample size in dose expansion.

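### The exact 80% interval for the expansion response rates ignores the futility looks, so 80% coverage is not guaranteed: it can fall to 72.1% (MRD+) or 76.0% (R/R)

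*SAP*

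**What the plan says.** SAP 9.5.2 states for R/R AML that "the proportion of subjects with an overall response with corresponding exact 80% CI will be calculated using the Clopper-Pearson method", by cohort and for everyone treated at the MTD/RP2D. For MRD+ AML it states that "the MRD conversion rate will be presented with corresponding exact 80% CI and tabulated by cohort and for all subjects treated at the MTD/RP2D". Protocol 10.5.3.2 plans the same, and SAP section 10 reports no departures from the protocol.

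SAP 3.3 and Protocol 10.3 set three futility looks in each expansion cohort.

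- R/R, planned size 40 ("FIH (R/R AML): approximately 40 subjects"): stop with 0 responses in 12, or if "2 or fewer of the initial 18 subjects treated experience a response", or with 3 or fewer in 24.
- MRD+, planned size 50 ("MRD Group (MRD+): approximately 50 subjects"): stop with 2 or fewer in 12, or if "4 or fewer of the initial 18 subjects treated experience a response", or with 5 or fewer in 24.

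SAP 3.2 and Protocol 10.2 give the expected precision at fixed sizes: 12% to 30% for a 20% rate in 40 subjects, and for MRD+, "With 50 subjects and a 40% response rate, the expected 80% CI would be 30.6% and 50.1" per cent. Neither document adjusts any of these intervals for the looks, or says that they are unadjusted.

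**The concern.** Clopper-Pearson is called exact because, at a fixed sample size, each tail error is at most 10%. Here the sample size depends on the responses: a cohort ends at 12, 18 or 24 precisely because its count is low. The fixed-sample limits take no account of that, so the 10% bound on the upper limit no longer holds.

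The direction matters. A cohort that stops through bad luck could be reported with an interval that appears to rule out a worthwhile rate, and could do so more often than the 80% label implies. The response and conversion rates are main measures for the secondary objective on anti-leukemia activity.

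**Working it through.** **Inputs.** Looks and boundaries from SAP 3.3; maximum sizes 40 and 50 from SAP 3.2; two-sided 80% level, 10% per tail, from SAP 9.5.2. Assumed: a crossed boundary always stops the cohort, and only expansion subjects are counted.

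**Formulas.** For x responses in n subjects, the Clopper-Pearson limits are L = Beta quantile(0.10; x, n−x+1) and U = Beta quantile(0.90; x+1, n−x). The exact probability of each outcome (stopping size n, count s) at true rate p comes from convolving binomials through the looks and removing stopped paths. Coverage at p is the sum of these probabilities over outcomes with L ≤ p ≤ U.

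**Reproducing the plan's figures.**
- 20/50 gives 30.6–50.1%, 8/40 gives 12.0–30.4% and 4/20 gives 9.0–36.1%, as in SAP 3.2. For 20/50, Wald (31.1–48.9%) and Wilson (31.6–49.1%) do not match, so the MRD+ figure is also Clopper-Pearson.
- R/R at 0.20: cumulative stopping 0.069/0.278/0.337, average size 32.5 (SAP Table 3: 0.07/0.28/0.34, 32.5).
- MRD+ at 0.35: 0.151/0.231/0.242, average size 41.4 (SAP Table 4: 0.15/0.23/0.24, 41.4).
- MRD+ at 0.25: 0.391/0.563/0.592, average size 28.9 (SAP Table 4: 0.39/0.56/0.60, 28.7). This small difference does not affect what follows.

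**MRD+ at a true rate of 0.40.**

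| Cohort ends at | Probability | Highest upper limit after a stop | Interval wholly below 0.40 |
|---|---|---|---|
| 12 | 8.3% | 38.6% (2/12) | 8.3% |
| 18 | 4.3% | 39.6% (4/18) | 4.3% |
| 24 | 0.4% | 35.2% (5/24) | 0.4% |
| 50 | 86.9% | n/a | 5.2% (15 or fewer responses) |

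The upper-tail error is 8.3 + 4.3 + 0.4 + 5.2 = 18.2%, against a nominal 10%. Intervals wholly above 0.40 (25 or more in 50) add 9.7%. Coverage is 72.05%; a simulation of 400,000 trials gave 72.06%. Every early-stop interval excludes 0.40. Given completion, coverage is 0.7205 / 0.869 = 82.9%.

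**MRD+ at other rates.** 88.3% at 0.25, 82.6% at 0.30, 85.5% at 0.35, 80.5% at 0.45 and 86.4% at 0.50. Coverage is below 80% only for rates of about 0.386 to 0.442.

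**R/R.** 78.7% at 0.20 (upper-tail error 12.7%), 86.0% at 0.25, 76.0% at 0.27 (upper-tail error 14.4%) and 83.4% at 0.30. It is below 80% only in narrow bands. At 0.27 every early-stop interval again misses: the upper limits are 17.5% (0/12), 26.9% (2/18) and 25.8% (3/24).

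**Without looks.** Coverage is 80.7% at 0.40 with n=50 and 83.7% at 0.20 with n=40. The minimum over rates is 80.3% (n=50) and 80.2% (n=40), so the shortfall comes from the stopping rule.

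**Interval that respects the design.** Stagewise ordering (an earlier futility stop ranks lower, then the count; 10% per tail) covers 81.3% for MRD+ at 0.40 and 84.5% for R/R at 0.20. Its minimum on a grid of 0.05–0.70 is 80.1% (MRD+) and 80.3% (R/R).

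| Result | Clopper-Pearson | Stagewise |
|---|---|---|
| 2/12 | 4.5–38.6% | 4.5–38.6% |
| 4/18 | 10.1–39.6% | 11.6–41.7% |
| 5/24 | 10.5–35.2% | 14.8–42.0% |
| 20/50 | 30.6–50.1% | 30.8–50.6% |
| 8/40 | 12.0–30.4% | 12.6–31.8% |
| 6/50 | 6.4–20.1% | 15.9–42.0% |

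**The case against.** **The 72.1% is the worst point.** This stands. A reader might infer that the interval under-covers in general. The enumeration does not support that: on a grid of 0.05–0.70 coverage averages 86.8% (MRD+) and 86.1% (R/R), and at the MRD+ futility threshold of 25% it is 88.3%.

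**The rates are illustrative.** This stands. SAP 3.2 uses 20% and 40% only to illustrate precision, not as targets. A reader might infer that both are worst cases. That is true of 40% for MRD+, but the R/R minimum is at 0.27, and at 20% the shortfall is 1.3 points.

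**These rates are not the only efficacy inference.** This stands. SAP 9.5.2 also plans Kaplan-Meier estimates with 80% intervals for duration of response, relapse-free survival and overall survival. No efficacy test is planned, and the primary endpoint is safety.

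**The result depends on assumptions.** This stands in part. SAP 3.3 only proposes stopping, and an override would bring coverage back toward the fixed-sample 80.7%; but SAP Tables 3 and 4 are computed as if stops are followed. The pooled MTD/RP2D interval may add escalation subjects. With an assumed 6 or 10 MRD+ subjects (the documents give no number), coverage at 0.40 is 78.8% or 82.9%. The by-cohort interval is still required, and there the problem remains.

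**The remedy has defects.** This stands against outright replacement. Stagewise limits equal Clopper-Pearson for stops at 12, so the 8.3% component is untouched. For rare low counts in a completed cohort they can exclude the observed rate: 6/50 is 12%, outside 15.9–42.0%.

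**Conclusion.** The concern holds in a limited form. The plan attaches a fixed-sample *exact 80%* label to expansion cohorts that can stop at three looks, so the coverage that the label implies is not guaranteed. It can fall to 72.1% for MRD+ (true rate 0.40; below 80% for about 0.39–0.44) and to 76.0% for R/R (true rate 0.27; 78.7% at 0.20). Elsewhere it is mostly at or above 80%.

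The effect sits mainly in intervals reported after an early stop; a completed cohort near the illustrated rates is barely affected. The lower limit is not the problem at these rates: intervals wholly above the true rate stay within 10%.

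The figures assume that futility stops are followed and only expansion subjects are counted. Pauses for DLTs, and subjects enrolled while responses are awaited, were not modelled. For secondary estimates in a phase 1 trial this is a modest point, worth correcting because correction is cheap.

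**What to change.** 1. In SAP 9.5.2 and Protocol 10.5.3.2, keep Clopper-Pearson for each expansion cohort, but call it nominal and unadjusted for the futility looks.
2. Report beside it an exact 80% interval that accounts for the stopping rule, for example by stagewise ordering with 10% per tail, and fix the ordering in the SAP.
3. In SAP 3.2 and Protocol 10.2, state that 12–30% and 30.6–50.1% are nominal and apply only if the cohort is not stopped for futility: about 66% of the time at R/R 20% (1 − 0.337) and 87% at MRD+ 40% (1 − 0.131).

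**Cost.** Wording and a short program; no extra subjects or data. Readers get a second interval that is sometimes much wider (5/24 goes from 24.7 to 27.2 points and shifts upward; 6/50 from 13.7 to 26.1 points), can exclude the observed rate at rare low counts, and changes nothing for stops at 12. That is why it should supplement Clopper-Pearson and not replace it.
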